DRUG USE INVESTIGATION FOR HIV INFECTION PATIENTS OF MARAVIROC

- HRD Joint Survey -

NON-INTERVENTIONAL (NI) STUDY PROTOCOL

Drug Use-results Survey of Celsentri Tablets 150 mg – HRD Cooperative investigation – Protocol

1. Objectives

To understand the following matters and to examine whether or not a special drug use-results survey and/or postmarketing clinical study is needed:

- Unknown adverse drug reactions (ADRs)
- Occurrence of ADRs under actual conditions of use
- Factors that are likely to affect safety, efficacy and other relevant matters

In addition, effects on immune competence, liver function and the cardiovascular system will be also evaluated as priority investigation items.

2. Planned Sample Size of the Survey and Rationale of Determination

Based on an approval condition, the drug use-results survey of Celsentri will be conducted in all patients treated with this drug at survey sites to the extent possible.

For the drug use-results survey implemented as part of the HRD cooperative investigation in which Celsentri is included, however, consideration will be paid by setting the upper limit of the number of patients to be enrolled at sites where there are many survey subjects for eliminating the influence of the present survey on routine medical practice at the sites and maintaining the quality of the survey due to this acute increase in the number of patients. When paying consideration, approximately 40 patients per investigator should be enrolled in the HRD cooperative investigation while taking account of time points for collecting case report forms (CRFs) and for case review by the investigator. If it is necessary of select subjects from all patients, consideration should be given so that there is no arbitrarily bias in efficacy or safety.

3. Subjects

The indication of Celsentri is as follows:

CCR5-tropic HIV-1 infection

The subjects of this survey will be patients who are prescribed with Celsentri (including retrospective patients).

4. Planned Number of Survey Sites by Medical Department

Institutions with which many physicians with a lot of experience in treatment are affiliated and which have many target patients (27 sites; Appendix 1).

5. Methods

A cooperative investigation (HRD cooperative investigation) by companies marketing drugs for the treatment of HIV infection^{Note 1)} will be conducted using a common CRF. The implementation of this survey will be outsourced to CMIC PMS Co., Ltd. (hereinafter referred to as the CRO). For the survey method, a central registration system will be adopted for sequentially understanding and controlling patients who used Celsentri.

In this survey, patient enrollment, input of data in survey items and data verification will be carried out using an Electronic Data Capture (EDC) system on the Internet from April 2009.

Some of the HRD cooperative investigation sites cannot connect to the external network so that the concerned sites shall lend a stand-alone computer (hereinafter referred to as the SPC), of which use is limited to the HRD cooperative investigation, and perform the survey.

5.1 Request for the Survey

(1) Request for the survey to physicians and conclusion of a contract

The CRO should request institutions collaborating in the survey to conduct the survey in writing and conclude a written contract.

(2) Request for the survey at the institutions concluded the contract

The CRO should fully explain physicians at institutions where the contract has been concluded, about the gist of the survey using the outline of the implementation of the HRD cooperative investigation, and given them a user's ID and password for the HRD cooperative investigation.

5.2 Patient Enrollment

(1) For patients who have been on drugs subject to the HRD cooperative investigation at the time of the contract or will start to receive them during the survey period, the investigator/subinvestigator should enter required information (medical record number or identification number, patient's initials [as necessary], gender, birth date [as necessary, age; e.g., age group], pregnancy status, inpatient/outpatient status, name of the drug surveyed and start date of treatment) on the enrollment screen of the EDC system, and send it using the user's ID and password issued for each investigator/subinvestigator. The patients' enrollment numbers will be issued by the EDC system. The sites that cannot connect to the external network should send or collect the data after inputting them in the SPC.

Patients who have been continuously on the drugs subject to the HRD cooperative investigation will be automatically continued to be enrolled based on data of the previous CRFs.

(2) The CRO should, as necessary, report the status of patient enrollment to the applicable companies using an HRD cooperative investigation control chart.

(3) Sites having a markedly high number of patients should first understand an expected number of new patients and then enroll new patients in the order of the re-enrollment of new patients on the day of enrollment in the HRD cooperative investigation among continuing patients and patient verification by the sites. The ratio of the number of re-enrolled continuing patients and newly enrolled patients should be adjusted. Overall, approximately 40 patients per investigator should be enrolled.

5.3 Progress Control of the Drug Use-results Survey

(1) The CRO should be aware of the progress of the survey at the study sites in charge to systematically promote it using the HRD cooperative investigation control chart.

(2) The Postmarketing Surveillance Control Manager should investigate whether or not the HRD cooperative investigation has smoothly progressed and, as necessary, give appropriate instructions to the CRO and relevant departments in the company.

5.4 Data Input/Sending and Reinvestigation

The investigator/subinvestigator should enter results up to the end of March of each year, in principle, between April and July and send them (Data will be collected using a USB memory device at sites where Internet communication is not available.). The CRO should request the investigator to perform a reinvestigation by gathering reinvestigations from each company. The CRO should print out the inputted and corrected CRFs from the EDC system. The investigator should check the contents and sign/seal them. These CRFs should be defined as the originals, and the CRO should send their copies to the applicable companies.

5.5 Statement of Confirmation on All-case Surveillance

The CRO should prepare a statement of confirmation collectively for enrolled patients by investigator and drug. The CRO should bring the statement of confirmation at the time of signing/sealing the originals of the CRFs, and the investigator should sign/seal the statement

of confirmation to ensure that the enrolled patients are all the treated patients. The CRO should send a copy (including fax) of the statement of confirmation signed/sealed by the investigator to the applicable company, and the CRO should retain the original.

5.6 Collection of Safety Information

The “HRD Cooperative investigation: Spontaneous Reporting Form for ADRs, etc.” should be distributed to all medical institutions where drugs for the treatment of HIV infection are used to collect safety information from physicians by fax.

- (1) At the time when the CRO visits the HRD cooperative investigation sites, safety information should be continuously collected even for patients who completed the patient enrollment period of the drug use-results survey using means such as the “HRD Cooperative investigation: Spontaneous Reporting Form for ADRs, etc.”
- (2) At institutions other than the HRD cooperative investigation sites, medical representatives (MRs) of each manufacturer should actively collect safety information.

5.7 Handling of Patients with ADRs

- (1) When ADRs, etc. (including those for which the causal relationship is unknown) suspected to be caused by the drug occurred, the investigator/subinvestigator should immediately notify them to the CRO or complete required information in the “HRD Cooperative investigation: Spontaneous Reporting Form for ADRs, etc.,” which has been provided beforehand, and fax it to the CRO.
- (2) When learning the onset of ADRs, etc. (including those for which the causal relationship is unknown) associated with Celsentri from healthcare professionals, an MR should immediately fill out the “HRD Cooperative investigation: Spontaneous Reporting Form for ADRs, etc.” and directly fax it to the CRO. When receiving a Spontaneous Reporting Form, it should be immediately faxed to the CRO.
- (3) When an anti-HIV infection drug, for which the causal relationship cannot be ruled out, was concomitantly used, an MR should obtain prior consent of the investigator for reporting ADR information to a company related to the concerned drug.
- (4) When identifying ADR information in data sent from the investigator, the CRO should notify it to the applicable company.
- (5) The applicable company should assess and analyze this ADR information and, as necessary, instruct a detailed investigation to the CRO. The CRO should request the investigator to input and send the latest information using the EDC system and inform it to the applicable company after receiving the said information.

6. Planned Period of the Survey

The survey will be started in April 2009. The patient enrollment period will be until the end of the 8th year.

Enrollment period: April 1, 2009 to March 31, 2017

7. Investigation Items

7.1 Identification Characteristics of the Investigators/Subinvestigators

Names of the site, department and investigator/subinvestigator, date of completing the form, and patient enrollment number

<HRD cooperative investigation: CRF>

7.2 Patient Background Characteristics

Medical record number, inpatient/outpatient status, patient’s initials, birth date, history of HIV infection treatment, race, gender, pregnancy status, infection route, underlying disease, date of

infection, past history, presence or absence of allergy, and presence or absence and details of complications

7.3 Prescribed Anti-HIV Drugs

Name of the drug, daily dose, duration of treatment and treatment continuation/discontinuation status

7.4 Prescribed Concomitant Medications (including drugs for the treatment of HIV-related diseases)

Presence or absence of prescribed concomitant medications, name of the drug, dose, duration of treatment, treatment continuation/discontinuation status and reason for use

7.5 Concomitant Therapies

Presence or absence of concomitant therapies, details of therapy, duration of therapy and reason for therapy

7.6 Patient Outcome (at discontinuation of the survey)

Date of outcome and details of outcome

7.7 HIV-RNA, CD4, CDC Classification, Time-course of Body Weight and Tropism

Date of test, number of HIV-RNA copies, CD4 count, CDC classification, body weight and tropism

7.8 Abnormal Changes in Laboratory Values

(i) Presence or absence of abnormal changes in laboratory values

(ii) Date of test

(iii) Hematology

White blood cell count, red blood cell count, hemoglobin, hematocrit, platelet count, differential white blood count, partial thromboplastin time (PTT), activated partial thromboplastin time (APTT), fibrinogen and fibrin degradation products (FDP)

(iv) Blood biochemistry

Total protein, albumin, total bilirubin, aspartate aminotransferase (AST) (glutamic-oxaloacetic transaminase, GOT), alanine aminotransferase (ALT) (glutamic pyruvic transaminase, GPT), lactic dehydrogenase (LDH), alkaline phosphatase (Al-P), gamma glutamyl transpeptidase (γ -GTP), creatine phosphokinase (CPK), blood urea nitrogen (BUN), creatinine, uric acid, total cholesterol, triglyceride, electrolytes, amylase, lipase, fasting blood glucose, C-reactive protein (CRP) and β_2 -microglobulin

(v) Urinalysis

Protein, sugar, occult blood and sediment

(vi) Abnormal ocular findings

7.9 Adverse Events (including ADRs, abnormal changes in laboratory values, new onset of opportunistic infection, etc.)

Presence or absence of adverse events (AEs), date of onset, diagnosis or name of specific symptom, details of symptoms/course and therapeutic action, seriousness, reason for assessing the event as serious, date of outcome, outcome, and relationship between disease and the drug used

(In the case of death) Presence or absence of autopsy, date of autopsy, autopsy findings and examination

7.10 Priority Investigation Items

In this survey, the occurrence of the following items will be defined as the priority investigation items:

(i) Effect on immune competence

[Reason for selection]

Nonclinical or clinical studies of Celsentri have not suggested that Celsentri treatment increases infections, malignancies, etc. However, there is a concern that Celsentri may affect immune competence (onset of infections, malignancies, etc.) based on its mechanism of action to inhibit CCR5 chemokine receptors.

[Investigation method]

By focusing on the onset of AEs such as infections and malignancies, they will be tabulated by the causal relationship with Celsentri and stratified according to patient background characteristics to evaluate the safety of Celsentri.

(ii) Effect on liver function

[Reason for selection]

No clinical data obtained so far shows the effect of Celsentri on liver function compared with placebo. However, a nonclinical study in rats revealed high exposure to the liver. CCI

Also, a Phase III study of Celsentri (A4001026) reported cases of liver disorder suspected to be related to maraviroc and resulted in liver transplantation.

[Investigation method]

By focusing on the onset of abnormal liver function test values and AEs mainly corresponding to hepatobiliary disorders according to the System Organ Class (SOC) of the MedDRA, they will be tabulated by the causal relationship with Celsentri and stratified according to patient background characteristics to evaluate the safety of Celsentri.

(iii) Effect on the cardiovascular system

[Reason for selection]

Clinical studies and a Phase IIb/III study to evaluate QT prolongation revealed no clinically significant effect on the QTc interval. In addition, the onset of myocardial infarction and ischemic heart disease during Celsentri treatment is rare, and their incidence is the same as that in this population with a history of treatment. However, nonclinical studies suggested that Celsentri might prolong the QT interval at concentrations above the therapeutic concentration.

[Investigation method]

By focusing on AEs mainly corresponding to cardiac disorders according to the SOC of the MedDRA, they will be tabulated by the causal relationship with Celsentri and stratified according to patient background characteristics to evaluate the safety of Celsentri.

A detailed investigation will be separately carried out in patients corresponding to the priority investigation items if the sponsor finds it necessary.

8. Analysis Items and Methods

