Attachment Form 2	Display the aggregation results of adverse reactions in <General Definitions> in accordance with the Safety Periodical Report Green Book. Overlapped adverse reactions with the same adverse reaction name (PT) in a patient should be counted as one event in accordance with <General Definitions> “Integration process”. Display the columns of “Cumulative results in Drug Use Result Survey” and “Total” only per “Survey period” provided in <General Definitions>. Leave the ‘status until approval’ column blank. Display System Organ Class (SOC) in the order of the international agreement and Preferred Terms in the order of encoded PTs.
Attachment Form 2-2 (Attachment Form 10 as the re-examination application document)	Display the aggregation results of serious adverse events in <General Definitions> in accordance with the Safety Periodical Report Green Book. Overlapped adverse events with the same adverse event name (PT) in a patient should be counted as one event in accordance with <General Definitions> “Integration process”. Display the columns of “Cumulative results” and “Total” only per “Survey period” provided in <General Definitions>. Leave the ‘status until approval’ column blank. Display System Organ Class (SOC) in the order of the international agreement and Preferred Terms in the order of encoded PTs. *Aggregate it with the number of patients in the special drug use survey for pregnant women.
*A list of adverse events	Prepare a list for adverse events in <General Definitions>. © Displayed items: [1] patient number, [2]repeat, [3] adverse event name (the reported name, and each code and the name of SOC, PT and LLT), [4] seriousness (company assessment, physician’s assessment), [5] expected/unexpected, [6] the first administration date of CELSENTRI Tablets, [7] the onset date, [8] days to the onset, [9] outcome, [10] relationship with CELSENTRI, [11] pediatrics (calculated), the elderly (calculated), renal disorder (calculated), liver disorder (calculated), pregnant women (calculated), each flag of haemophilia (calculated), male/female patient, patient’s age

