*A list of adverse reactions per patient background, etc.	Prepare a list for adverse reactions in <General Definitions>. © Displayed items: No., patient registration number, age, pediatrics, the elderly, race, presence/absence of pregnancy, presence/absence of complications, haemophilia, renal disorder, hepatitis A, hepatitis B, hepatitis C, others, liver disorder, syphilis, others, presence/absence of haemophilia, presence/absence of liver disorder, presence/absence of renal disorder, name of complication, presence/absence of allergy, presence/absence of concomitant treatment, name of concomitant treatment, presence/absence of concomitant drugs, number of concomitant drugs, presence/absence of concomitant anti-HIV drugs, number of concomitant anti-HIV drugs, administration period, long-term administration, presence/absence of adverse events, presence/absence of adverse reactions, name of adverse reactions (PT), seriousness, outcome, days to the onset, relationship with CELSENTRI
Incidence of adverse reactions per patient background	Prepare a table of incidence of adverse reactions on the following patient-background items: Follow the above <<Handling of Items>> for the definitions of each item per background. © Displayed items: primary disease, sex, presence/absence of pregnancy, age, inpatient/outpatient classification, treatment history of HIV infection, race, route of transmission, duration of disease, medical history, allergy, complication, type of complication, renal disorder, liver disorder, the mean daily dose, administration period, administration period [cumulative], total dose, total dose [cumulative], continued/discontinued, concomitant drug, number of concomitant drugs, type of concomitant drugs, number of concomitant anti-HIV drugs, type of concomitant anti-HIV drugs, presence/absence of CYP3A inducer, presence/absence of haemophilia, haemophilia AB, CDC classification of severity prior to administration, tropism classification at the first administration, concomitant treatment, blood coagulation factor (all cases and the cases with haemophilia) Calculate the minimum and the maximum for age, duration of disease, the mean daily dose, administration period, total dose while calculate the

	mean and the standard deviation for age as well (Of note, as to the description age for example, calculate the age of a patient in his 30s will be calculated as 30 years old).

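### The SAP names no table for the three priority investigation items, so the analysis promised in Protocol 7.10 is only partly covered

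*Protocol*

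**What the plan says.** Protocol section 1 (Objectives) states that "effects on immune competence, liver function and the cardiovascular system will be also evaluated as priority investigation items". Section 7.10 then gives a method for each item and says of the events in all three that "they will be tabulated by the causal relationship with Celsentri and stratified according to patient background characteristics":

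- Immune competence: "By focusing on the onset of AEs such as infections and malignancies, they will be tabulated by the causal relationship with Celsentri".
- Liver: "By focusing on the onset of abnormal liver function test values and AEs mainly corresponding to hepatobiliary disorders", again tabulated by causality and stratified by background.
- Cardiovascular: "By focusing on AEs mainly corresponding to cardiac disorders according to the SOC of the MedDRA", with the same tabulation and stratification.

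Section 7.10 adds: "A detailed investigation will be separately carried out in patients corresponding to the priority investigation items if the sponsor finds it necessary". That work is at the sponsor's discretion and comes on top of the tabulation.

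The SAP lists its safety outputs under Type of Tables, 3). For Attachment Form 2 the instruction is "Display the aggregation results of adverse reactions in <General Definitions> in accordance with the Safety Periodical Report Green Book". For the main background analysis it is "Prepare a table of incidence of adverse reactions on the following patient-background items". Under General Definitions, adverse reactions are the events that the company could not dissociate from the drug. AEs are the wider class, which also includes unrelated events. The SAP text never mentions the priority investigation items.

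**The concern.** Section 7.10 speaks of AEs, not adverse reactions. A split by causal relationship only makes sense if unrelated events are in the table. If the SAP is followed exactly, the background-stratified results contain only events that the company assessed as possibly related.

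This matters most for the immune item. The protocol says that this concern rests on the drug's mechanism and not on an earlier clinical finding. Infections and malignancies in people with HIV have other plausible causes, so individual cases may readily be assessed as unrelated. A table limited to related events then depends heavily on case-by-case attribution, and the protocol's method avoids that by showing both classes.

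For the liver item, the protocol cites suspected cases that led to transplantation and asks for abnormal test values, yet the SAP names no such table. Without agreed event groupings, anyone assembling the priority-item results later would have to choose the terms with the data in hand.

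**Working it through.** No arithmetic applies beyond a count of coverage. The check sets what section 7.10 asks for (AEs of any causality, split by causality, stratified by background, grouped by item, with liver tests) against each relevant SAP output.

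| SAP output | Events counted | Causality split | Background strata | Priority grouping |
|---|---|---|---|---|
| Attachment Form 2 | Adverse reactions | Related only | None stated | SOC/PT rows only |
| Attachment Form 2-2 | Serious AEs, pooled with the pregnancy survey | None stated | None stated | SOC/PT rows only |
| List of adverse events | All AEs | Relationship shown per line | Age, sex and a few flags | None; a listing without denominators |
| Incidence of adverse reactions per patient background | Adverse reactions | Related only | Full set of rows | None stated |
| List of onset status of adverse reactions/infections per background | Adverse reactions; infections part not defined | None stated | Most of the same rows | None named for malignancy, liver or heart; row layout not shown |
| Incidence per concomitant drug and per complication | Adverse reactions | Related only | One factor each | None stated |
| HIV-RNA and CD4 table and chart | Laboratory values (efficacy) | Not applicable | Several subgroups | Not applicable |

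**Which events reach a summary table.** Cross-classify AEs by seriousness and relationship, which gives four cells. Form 2 covers the two related cells. Form 2-2 covers the two serious cells. The fourth cell, non-serious and unrelated, is in no summary table and appears only in the line list. As described in the SAP, Form 2-2 also does not separate serious related from serious unrelated events.

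**Which events are stratified by background.** The incidence table by background covers only the related cells and states no breakdown by priority item. The line list cannot fill the gap by itself: it gives no denominators, and its displayed fields omit treatment history, CDC class, concomitant drugs and tropism, all of which are rows of the incidence table.

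**Liver tests.** Protocol 7.8 collects AST, ALT, bilirubin, alkaline phosphatase and γ-GTP. The only laboratory tables in the SAP are HIV-RNA and CD4. Liver disorder in the SAP is a baseline complication used as a stratum, not an outcome. Liver test abnormalities reach the safety outputs only if reported and coded as AEs, which Protocol 7.9 allows.

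**Count over the three items.**

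- Related events visible by SOC/PT: 3 of 3 (Form 2).
- Serious events visible by SOC/PT: 3 of 3 (Form 2-2).
- Dedicated table named: 0 of 3.
- Summary of AEs by causality within the item: 0 of 3.
- Stated background stratification of all-causality AEs within the item: 0 of 3.

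**The case against.** The strongest reply is that much of the information is already there. Forms 2 and 2-2 show related and serious events by SOC and PT, so infections, neoplasms, hepatobiliary and cardiac events of those kinds appear in tables. The line list holds every AE with its SOC, PT and relationship. Protocol 8.2 makes adverse reactions the primary safety analysis, and the SAP follows it. This stands, and it limits the point: a reader might infer that the objective goes unanswered or that no priority item has any output, and the documents do not support either reading.

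Three further replies carry some weight.

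- The SAP relies on mock-ups that are not among the documents, and it says that table forms may change. A priority-item layout there cannot be excluded. Still, the SAP's own list of tables should name it.
- The list of adverse reactions/infections by background might partly serve the immune item. The SAP ties only the adverse-reaction part to its definition, leaves the infections part undefined and does not show the rows. It would be wrong to say that the infections part is limited to related events. It would be equally wrong to count it as the promised table.
- The survey has no comparator, and 7.10 promises a tabulation, not a formal test. That bears on how the tables are interpreted, not on whether they are owed.

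A reader might also infer that the cardiac item shuts out QT findings, because it refers to one SOC while its rationale concerns QT prolongation. The text does not say so. The word *mainly* leaves room for terms coded elsewhere, and what is missing is a statement of which terms count.

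**Conclusion.** The gap between protocol and SAP is real, but it is one of partial coverage. The SAP text names a dedicated table for 0 of 3 priority items. Related and serious events can be seen by SOC and PT. The missing pieces are the split of all AEs by causality within each item, the background stratification of unrelated events, any summary of non-serious unrelated AEs, a table of liver test abnormalities, and the term lists that define the items.

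The number of events affected cannot be estimated, because the documents give neither the share of AEs assessed as unrelated nor the share that is non-serious. The conclusion does not depend on those shares. It assumes that the unseen mock-ups and matching specification contain no priority-item table. If they do, the remedy reduces to naming that table in the SAP. The change should be made, because following the SAP as written would omit an analysis that the protocol commits to.

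**What to change.** Under Type of Tables, 3), on the safety analysis set, add one table per priority item. Each should give the number and percentage of patients with events as related, not related and total, by the background rows already listed for the incidence of adverse reactions. Two details need wording. State how a patient with both related and unrelated events in the same item is counted, since the columns need not add to the total. Adapt the cumulative duration and cumulative dose rows, which the SAP defines by time or dose to an adverse reaction.

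Before output, fix and document the MedDRA SOC/PT list for each item:

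- infections and malignancies;
- the hepatobiliary SOC plus the abnormal liver test terms that count;
- the cardiac SOC, stating whether reported QT or ECG terms coded elsewhere count under *mainly*.

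The cost is SAP wording and three tables from data already collected and coded. Many strata will be sparse, so the tables should be read descriptively. The SAP records the data lock as March 26, 2018. Term lists may therefore be fixed after lock; if so, record the date and say so. In that case the gain is traceability, not full pre-specification.
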